Subjects who experience a flare or subjects who cannot adhere to the protocol-defined steroid taper due to a flare should be managed to ensure the best possible care of the subject:

- The subject must discontinue the assigned study drug (KPL-301 or placebo) and should receive escape therapy in accordance with local SoC, as determined by the Investigator, which may include, for example, dose modifications of corticosteroids, other immunomodulatory agents, and/or approved therapies (e.g., tocilizumab). The dosages of all concomitant medications used to treat the GCA flare must be entered into the eCRF.
- Escape corticosteroid therapy can be escalated immediately. Due to possible safety and pharmacologic effects resulting from overlapping exposures to immunomodulatory agents on top of co-administered corticosteroids, the investigator should consider a washout period of at least 35

days (based on elimination half-lives) after the last dose of study drug if deemed clinically appropriate.

Any subject who prematurely discontinues the study drug treatment for safety or other reason will have an End-of-Treatment (EOT) visit and will be followed for the intended duration of study treatment (i.e., through Week 26 and Washout Safety Follow-up) to address potential issues of informative censoring. Any subject who withdraws consent from the trial (i.e., all study procedures in addition to study drug administration) must complete at a minimum the Final Washout Safety Follow-up visit 84 ± 3 days from the last dose administered. Additional follow up using public records may be captured where possible.

Washout Safety Follow-up:

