After subjects complete the 26-week double blind treatment period, they will discontinue and wash off of blinded KPL-301 or placebo during a 12-week Washout Period, which includes close safety follow-up and monitoring for potential GCA flares. During this time, it is recommended that subjects, regardless of remission status, receive SoC oral prednisone therapy, taking into consideration that they have just completed treatment with what may have been an efficacious therapy which supported the tapering off of standard of care concomitant oral corticosteroids. Clinicians may choose to observe subjects closely during the washout period without any change in concomitant medications or may choose (consistent with current SoC guidelines) to increase the daily corticosteroid dose prophylactically/empirically by approximately 10 mg above the prednisone dose administered at Week 26. The prednisone dose can then be tapered, increased or maintained throughout the remainder of the 12-week Washout Period as per Investigator discretion. After the Final Washout Safety Follow-up visit (Week 38) has been completed, the subjects will exit the trial and should be transitioned to SoC per investigator judgement. It is not required that the steroid taper have been completed (0 mg) prior to subjects exiting the trial at Week 38.

Number of Subjects:

Approximately 70 subjects will be randomized at a 3:2 allocation ratio. Approximately 42 subjects will be assigned to KPL-301, and approximately 28 subjects will be assigned to placebo. Of the study population, the aim is to have 50% with new-onset disease and 50% with relapsing disease.

Eligibility Criteria:

Inclusion Criteria

1. Able and willing to provide written informed consent and to comply with the study protocol
2. Age of ≥ 50 to 85 inclusive
3. Diagnosis of new-onset or relapsing GCA classified according to the following criteria:

New-onset: Initial diagnosis of GCA within 6 weeks of Day 0, defined as:

- a) Westergren ESR > 30 mm/hour or CRP ≥ 1 mg/dL
- b) AND at least one of the following:
 - i. Unequivocal cranial symptoms of GCA (new-onset localized headache, scalp or temporal artery pain or tenderness, ischemia-related vision loss, or otherwise unexplained mouth or jaw pain upon mastication)
 - ii. Unequivocal extracranial symptoms of GCA such as claudication of the extremities
 - iii. Symptoms of PMR, defined as shoulder and/or hip girdle pain associated with inflammatory morning stiffness

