### **1.3. Sample Size Justification**

The sample size calculation was based on the assumption that time to flare follows an exponential distribution and the proportion of subjects without a flare by week 26 will be 50% in placebo and 85% in KPL-301, the median time to flare would be approximately 26 weeks in placebo arm and 111 weeks in KPL-301 arm. The hazard ratio (KPL-301 vs. placebo) would be approximately 0.234. With a 2-sided significance level of 0.05 and a 3:2 randomization ratio for KPL-301 vs. placebo, it would require approximately 20 events to achieve 87% power using a two-sided log rank test.

Approximately 70 subjects will be randomized by disease stratum (new-onset or relapsing/refractory) to receive KPL-301 or placebo at a 3:2 allocation ratio.

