### **6.8.1. Adverse Events**

An adverse event (AE) is any untoward medical occurrence in a subject or clinical investigation subject administered a pharmaceutical product. An AE does not necessarily have a causal relationship with this treatment. Drug-related AEs will be considered those to be at least possibly related to investigational product based on the investigator's assessment.

Treatment emergent AEs (TEAEs) is defined as AEs that begin after the first administration of investigational products or existing AEs that worsen after the first dose of study medication through the 90 days after the last dose date.

TEAEs will be coded using MedDRA version 21.0. A summary of the frequency (number and percentage of subjects) of TEAEs will be presented by system organ class (SOC) and preferred term (PT) by treatment, in decreasing frequency of SOC and PT in the KPL-301 arm. The TEAE will also be analyzed by their severity (mild, moderate or severe), relationship to study drug, leading to death, resulting in dose interruption, leading to withdrawal of study treatment. Treatment emergent serious AEs (TESAE), drug related TESAEs, TEAE of special interest (TEAESI) will also be tabulated.

An adverse event of special interest (AESI) is one of scientific and medical interest specific to understanding of the Investigational Product and requires close monitoring and rapid communication by the investigator to the sponsor. An AESI may be serious or non-serious. AESI are defined in Section 13.1.3 of the protocol.

A subject experiencing the same AE multiple times will be counted only once for that preferred term. Similarly, if a subject experiences multiple AEs (preferred terms) within the same system organ class, then that subject will be counted only once for that system organ class. When summarizing by severity and relationship, only event with highest severity or relationship will be counted.

Tables will include the following details:

- Overview of TEAEs (summary from all the subsequent tables)
- TEAEs by severity
- Drug related TEAEs
- TESAEs
- Drug related TESAEs
- Non-serious TEAEs
- TEAESI
- TEAEs leading to permanent discontinuation of study drug
- TEAEs leading to dose interruption
- TEAEs resulting in deaths.

All AEs and SAEs occurring throughout the conduct of the study, including all-cause deaths, will be displayed in listings.

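### Adverse events are tabulated only as percentages of subjects, although a flare closes the reporting window early, so the arms are not compared over equal time at risk and the direction of the error is unknown

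*SAP*

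**What the plan says.** SAP 6.8.1 sets out the adverse event tables: "A summary of the frequency (number and percentage of subjects) of TEAEs will be presented by system organ class" and preferred term, by treatment. Each subject counts once per term. Serious events, events of special interest (AESIs), drug-related events and the other listed tables follow the same pattern. Protocol 14.6.1 also specifies number and percentage. Neither document plans a rate per patient-year, a time-to-first-event analysis or a common fixed window.

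The SAP ends the window "through the 90 days after the last dose date". SAP 7.1 lists this as a change; the definition in Protocol 14.6.1 has no end tied to the last dose.

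On a flare, the Protocol Synopsis says: "The subject must discontinue the assigned study drug (KPL-301 or placebo) and should receive escape therapy in accordance with local SoC". Protocol 8.4.1, 10.3 and 11.2 repeat this. Protocol 10.3 names high-dose or intravenous corticosteroids, other immunomodulatory agents and tocilizumab as examples of escape therapy.

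SAP 1.3 assumes that "the proportion of subjects without a flare by week 26 will be 50% in placebo and 85% in KPL-301".

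SAP 6.6.1, 6.6.4 and 6.6.6 summarise treatment duration, number of injections and escape therapy by arm. None of these is used as a denominator for adverse events.

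**The concern.** A flare stops the drug, the last dose fixes the end of the TEAE window, and the plan expects more than three times as many flares on placebo, proportionately, as on KPL-301 (50% against 15%). Placebo subjects are then watched for less time on average, and a percentage of subjects with an event rises with time watched.

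A second effect runs the other way. Up to 90 days after the last dose, events that occur under escape therapy still count for the assigned arm. Most of that time belongs to placebo, and escape therapy may itself raise the event rate.

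Safety and tolerability is a named secondary objective, and these tables are its main evidence. As planned, they mix any drug effect with unequal follow-up and with the effects of escape therapy, and the reader cannot separate the three.

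**Working it through.** **Inputs from the documents.** Flare-free proportion S at Week 26: 0.50 placebo, 0.85 KPL-301, exponential (SAP 1.3). Arm sizes 28 and 42 (Protocol Synopsis). Window end: last dose + 90 days = 90/7 = 12.86 weeks (SAP 6.8.1). Dosing every 2 weeks (Protocol 9.5).

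**Assumed, not in the documents.** The adverse event rate, its shape over time, and the effect of escape therapy on it.

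**1. The plan's own figures.**
- Hazard ratio = ln(0.85)/ln(0.50) = 0.2345, against the stated 0.234.
- KPL-301 median = 26 × ln 2 / (−ln 0.85) = 110.9 weeks, against the stated 111.
- Power with 20 events at 3:2 (k = 1.5), Freedman: z = √(20 × 1.5) × (1 − 0.2345)/(1 + 1.5 × 0.2345) − 1.96 = 1.14, so 87.4%, against the stated 87%. Schoenfeld's formula gives 88.9%.
- Expected flares = 28 × 0.50 + 42 × 0.15 = 20.3.

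**2. Time on drug.** With λ = −ln(S)/26, mean time to flare or Week 26 = (1 − S)/λ.
- Placebo: 0.50/0.02666 = 18.8 weeks.
- KPL-301: 0.15/0.00625 = 24.0 weeks.

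**3. TEAE window.**
- Adding 12.86 weeks gives 31.6 and 36.9 weeks.
- Using the last two-weekly dose before flare, and a cap at Week 38, gives 30.7 and 36.0 weeks (ratio 1.17).
- With 50% flare-free in both arms, the windows are equal.

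**4. Crude percentage at an equal constant rate r.** Mean of 1 − exp(−r × window), using the windows of 31.6 and 36.9 weeks:

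| Rate per patient-year (assumed) | Placebo | KPL-301 | Excess, points |
|---|---|---|---|
| 0.05 | 3.0% | 3.5% | 0.5 |
| 0.1 | 5.9% | 6.8% | 0.9 |
| 0.5 | 25.9% | 29.6% | 3.8 |
| 1 | 44.6% | 50.3% | 5.7 |
| 2 | 68.3% | 75.0% | 6.7 |

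The two-weekly, capped windows give 0.5 to 7.0 points over the same rates.

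**5. Front-loaded risk.** With equal hazards that decline exponentially (assumed decay constant 8 to 13 weeks, 38-week risk 10% to 80%), the excess falls to about 0.2 to 2 points.

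**6. Escape therapy.** Mean post-flare time inside the capped window is 5.9 weeks on placebo and 1.8 on KPL-301. If the event rate after flare is m times the rate before, expected counts balance at m ≈ 1 + (35.98 − 30.68)/(5.94 − 1.78) = 2.27. With the windows of step 4 and 1 event per patient-year, the KPL-301 excess is +5.7 points at m = 1, +0.9 at m = 2, −1.2 at m = 2.5 and −5.9 at m = 4.

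**7. Against sampling error.** Near 50%, the standard error of the difference is √(0.25/28 + 0.25/42) = 12.2 points. The shift there is 5.7/12.2 = 0.47 of a standard error.

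**8. Does person-time alone repair it?** At equal constant rates, events per unit of person-time at risk give a rate ratio of 1.00. Under the declining hazards of step 5, the KPL-301/placebo ratio is about 0.87 to 0.93 although the true hazards are equal, because the longer KPL-301 window adds late, low-risk time.

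**The case against.** The strongest reply is that this is a descriptive safety summary in a proof-of-concept study of about 70 subjects. No adverse event test is planned, exposure and escape therapy are tabulated by arm, all adverse events are listed, and the sponsor could derive rates later. The shift is well inside sampling error, and for serious events or AESIs, if they are rare, it is well under one subject in 42. All of that stands, and it limits the weight of the point. It does not make the percentages comparable: a separate exposure table does not correct an incidence table, and an error that comes from the window definition does not shrink with more subjects.

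Two stronger readings are tempting.
- A reader might infer that the tables are biased against KPL-301. The documents do not support a direction. The excess requires that flare and escape therapy leave the event rate unchanged, and the permitted escape regimens make that doubtful. It also requires a roughly constant hazard, whereas every subject starts prednisone at 20 to 60 mg/day and tapers (Protocol 9.3, Table 3), so steroid-related risk may well fall early.
- A reader might infer that the windows are unequal whatever happens. They differ only if KPL-301 delays flare, or if discontinuations for other reasons differ by arm; the calculation ignores the latter.

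The objection that exposure-adjusted rates are not a neutral cure is correct and changes the remedy.

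**Conclusion.** The point holds as one of comparability, not of direction. On the plan's own flare assumptions, the mean TEAE window is about 5 weeks longer on KPL-301, and the planned percentages do not allow for it. The size depends on assumed event rates: under 1 point for rare events, 4 to 7 for common ones at a constant hazard, about 2 or less if risk is front-loaded, and zero or reversed if the event rate after flare is about 2.2 to 2.3 times higher or more. The practical risk is that the tables could either overstate or mask harm from KPL-301, and nothing in them shows which. This is a cheap improvement to make before unblinding, not a defect that invalidates the safety analysis.

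**What to change.** Keep the crude tables. In SAP 6.8.1, for all TEAEs, serious TEAEs and AESIs, add:

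- (a) patient-years at risk, counted to first event or window end, and exposure-adjusted incidence rates by arm;
- (b) TEAEs with onset before and after first escape therapy, shown separately, each with its own time at risk;
- (c) because (a) assumes a constant hazard, either a Kaplan-Meier summary of time to first event or percentages over a common window from first dose to Week 38.

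Option (c) over Week 38 relies on the Table 1 footnote that asks subjects who stop treatment to keep attending their remaining visits. Protocol 13.4 ends adverse event collection 84 ± 3 days after the EOT visit, which for an early stopper can fall before Week 38. The two should be reconciled with each other and with the 90-day rule. If collection does stop early, use the Kaplan-Meier form, censored at the end of collection.

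The cost is a few extra descriptive tables from adverse event, dosing and escape-therapy data that the study already collects. No new assessment and no change to the efficacy analysis is needed.

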#### **6.8.2. Clinical Laboratory Parameters**

Laboratory assessments should be collected as per the schedule of assessments, starting at Screening, Baseline, Week 4, Week 12, Week 20, Week 26/EOT, and Final Safety Follow-up/Week 38.

Unscheduled laboratory assessments for safety issues are permitted as deemed necessary by the Investigator. Local laboratory tests and values may be used by the Investigator as necessary to support clinical decisions.

Clinical laboratory assessments are listed in [Table 3](#).

**Table 3: Clinical Laboratory Assessments**

Clinical chemistry:	Hematology:	Urinalysis:
Alanine aminotransferase (ALT)	Hemoglobin	Bilirubin
Albumin	Mean corpuscular hemoglobin concentration	Blood
Alkaline phosphatase (ALP)	Mean corpuscular volume	Creatinine
Apolipoprotein A	Platelet count	Glucose
Apolipoprotein B	Red blood cell (RBC) count	Ketones
Aspartate aminotransferase (AST)	White blood cell (WBC) count	Leukocyte esterase
C3	WBC differential (total and percentage):	Nitrite
C4	Basophils	pH
Calcium	Eosinophils	Protein
Chloride	Lymphocytes	Specific gravity
Creatinine	Monocytes	Urobilinogen
Creatinine phosphokinase	Neutrophils	
Glucose		
HbA1c		
High-density lipoprotein		
Low-density lipoprotein		
Phosphorus		
Potassium		
Sodium		
Total bilirubin (direct and indirect will be performed if total bilirubin is greater than the ULN)		
Total Cholesterol		
Total protein		
Triglycerides		
Urea		
Uric acid		

**Other:**

Serum pregnancy test prior to randomization

Urine pregnancy test at Day 0, Week 12, Week 26 and the Final Washout Safety Follow-up Visit.

Continuous laboratory data will be examined for trends using descriptive statistics of actual values and changes from baseline over time in each treatment group. These data will also be categorized as low, normal or high based on the reference ranges of the central laboratory. Shift tables from baseline to worst post baseline time point will be presented. In shift tables from baseline to worst

post-baseline value, the worst value post baseline within a subject will include both scheduled and unscheduled visits. In each shift table, the denominator of the percentage in a cell within a baseline category (e.g., normal) will be the total number of subjects in each treatment group in the category at baseline.

Biochemistry and hematology lab tests will be assessed relative to laboratory normal ranges (low, normal, high). Shift from baseline to the worst grade on study, and from baseline to by visit reference will be presented. Shifts from baseline to worst value on study will be presented for categorical or ordinal lab parameters. Incidence of subjects with laboratory values outside laboratory supplied normal range will also be presented.

All biochemistry and hematology results will be presented in by-subject listings. Urinalysis results will be summarized by categoricals and will also be presented in the listing.

### **6.8.3. Vital Signs**

Vital signs including measurements of weight, respiratory rate, pulse rate, systolic and diastolic blood pressure, and temperature will be measured at each scheduled study visit starting from Screening. Blood pressure measurements should be obtained after the subject has been seated for at least 5 minutes. Body weight and BMI will also be included.

Vital signs will be summarized using descriptive statistics of actual values and changes from baseline over time and by treatment group.

All vital signs assessments will be listed appropriately.

### **6.8.4. Electrocardiogram**

ECG variables will be summarized using descriptive statistics for each treatment group at Screening and post-baseline visit (unscheduled) for the following:

- QT
- RR
- PR
- QRS
- Heart Rate

Number and percent of subjects with normal, not clinically significant abnormal, and clinically significant abnormal results for the 12 lead ECG will be tabulated by treatment group at Screening. ECG assessments will be performed only at Screening, with the exception of unscheduled assessments.

All ECG data will be listed in by-subject listings.

### **6.8.5. Physical Examination Findings**

A complete physical examination includes at minimum evaluation of vital signs, head, eye, ear, nose, and throat as well as cardiovascular, dermatological, musculoskeletal, respiratory, gastrointestinal, genitourinary, and neurological systems. Physical examination assessments will be measured at Screening and Week 26/EOT.

Physical examination findings will be summarized by visit. The number and percentage of subjects with normal, abnormal not clinically significant and abnormal clinically significant findings will be presented for each body system.

New or worsened physical examination abnormalities following treatment will be recorded as AEs and will be reflected in the summary of AEs.

All physical examination findings will be presented in by-subject listings.

## **7. CHANGES TO PLANNED ANALYSES FROM THE PROTOCOL**

### **7.1. Changes from Protocol**

- The protocol stated the first administration of subcutaneous KPL-301/placebo and oral prednisone taper will take place at the study site on Day 0. In this SAP, we defined the first administration of subcutaneous KPL-301/placebo as Day 1. The start date of the oral prednisone taper is not included the definition of Day 1 since not all patients took the first dose of subcutaneous KPL-301/placebo and oral prednisone taper on the same day.
- TEAE definition was updated to include AE through last dose + 90 days.
- CM definition was updated to include medications through last dose + 90 days.
- Included PFTs, DLCO, Dyspnea score, O2 saturation in safety endpoints.
- The protocol described the categories of cranial symptoms as follows. [Section 6.7.2](#) of this SAP adopts the abbreviated categories from the eCRF.
  - New or recurrent headache or pain or tenderness of the scalp or the temporal artery

- Visual signs/symptoms such as ischemic retinopathy, optic neuropathy, diplopia, amaurosis fugax, etc.
- New or recurrent claudication of the tongue, masseter muscle, or worsening temporal artery signs and symptoms
- Transient ischemic attack (TIA) or stroke related to GCA in the opinion of the Investigator
- The protocol described the categories of extracranial symptoms as follows. Section 6.7.2 of this SAP adopts the abbreviated categories from the eCRF.
  - Classic PMR-like symptoms, defined as shoulder and/or hip girdle pain associated with inflammatory morning stiffness
  - New or recurrent claudication in the peripheral circulation (i.e., in one of the extremities)

## 7.2. Impact of Covid-19 pandemic

The impact of the pandemic to the study conduct is expected to be limited as assessed by the amount missing data due to lack of office visits or other COVID-19 related issues with the conduct of the trial. Therefore there are no special data handling rules and analyses implemented for COVID-19 related protocol deviations. A separate document will be prepared to summarize any protocol deviations which occurred as a result of the pandemic.

## 9. APPENDICES

### 9.1. Handling of Missing Safety Data

No imputation will be made for completely missing date unless otherwise specified. General imputation rules mentioned below apply to partially missing or impossible dates:

- If the stop date is not missing, and the imputed start date is after the stop date, the start date will be imputed by the stop date
- If the start date is not missing, and the imputed stop date is before the start date, then the imputed stop date will be equal to the start date
- Any imputed dates need to be logical. For example, last dose date should not be later than death date.

When imputation rules in subsequent sections contradicts the general rule, always follow the general rule.

#### 9.1.1. Adverse Event Date Imputation

Follow the general rule specified in Section 9.1.

##### **Incomplete Start Date:**

*Missing day, month, and year*

No imputation will be made; the corresponding AE will be included.

*Missing day and month*

- If the year is the same as the year of the first dose date, then impute day and month as the day and month of the first dose
- If the year is prior to the year of the first dose date, then impute day and month as 31 Dec
- If the year is after the year of the first dose date, then impute day and month as 01 Jan.

*Missing day only*

- If the month and year are the same as those of the first dose date, then impute day as the day of the first dose date
- If either the year of partial date is before the year of the first dose date, or the years are the same, but the month of partial date is before the month of the first dose date then impute day as last day of the month
- If either the year of partial date is after the year of the first dose date, or the years are the same, but the month of partial date is after the month of the first dose date, then impute day as first day of the month.

